# **10.4.5 Body weight** (consider supplemental feeding if nutrition compromised)

Loss of body weight greater than 20 % compared to body weight at the end of radiotherapy

(or earlier if long term corticosteroids have been needed)

Reduce CCNU in next course to 50 mg/m^2

If further loss of body weight

Omit CCNU for next and all subsequent courses

# 10.5. Supportive Care during chemotherapy.

• **Anti-emesis:** A 5HT3 antagonist must be used as an anti-emetic for cisplatin-containing chemotherapy.

Dexamethasone should not be used as an anti-emetic unless other therapies fail.

• Steroids: Pa

Patients should not be receiving steroid therapy (e.g. dexamethasone) during chemotherapy if at all possible. If symptoms of raised intra-cranial pressure develop during treatment the cause e.g. hydrocephalus should be actively sought. Steroids should be used as a short-term measure prior to definitive treatment of the raised pressure.

# 11. FOLLOW-UP AFTER TREATMENT

# 11.1 Oncological Follow-up

- Clinical follow-up at centre discretion.
- Neuroradiological follow-up:

For purposes of this study, MRI of head and spine should be performed at least every 6 months for 3 years post treatment. Other imaging is to be performed at the treating physician's discretion.

# 11.2 Late effects: see Appendix M and table in section 1.5.

# 11.3 Relapse or Death

> Tumour relapse or patient death must be notified to the National Data Centre using the appropriate Data Form within one month of the event.

- ➤ In the case of sudden death due to a SAE this must be reported within 24 hours of knowledge of the event as with other SAEs (see section 12).
- In the event of a relapse that involves the Posterior Fossa, then the appropriate National Radiotherapy QA Group must be informed.
- > Spinal MR should be performed in the event of a Posterior Fossa relapse to define fully the pattern of relapse and to plan further therapy.
- ➤ Guidance for the treatment of relapse can be obtained from the appropriate PNET 4 National Co-ordinator.

### 12. SERIOUS ADVERSE EVENTS AND TOXICITY REPORTING.

## Common Toxicity criteria definitions will be used for toxicity reporting.

The CTC (Appendix L) used in completion of the data forms will be the same for all participating groups.

Definition of serious adverse events (SAEs) is based upon the ICH GCP Guidelines

In this study, a serious SAE is defined as:

Any unexpected medical occurrence that:

- Results in death (death from tumour progression is not an SAE)
- Is life-threatening
- Requires unexpected inpatient hospitalisation or prolongation of existing hospitalisation
- Results in persistent or significant disability/incapacity
- Overdose that leads to symptomatic disease

In addition, for this study the following toxicities will also be defined as SAEs:

- Any grade 3 or grade 4 central neurotoxicity
- Any grade 3 or grade 4 unexpected toxicity

Ototoxicity as a result of cisplatin chemotherapy and radiotherapy to the cochlea is an expected complication of the treatment described in this protocol. As such, ototoxicity, including Grade 3 or 4 ototoxicity, is not regarded as a SAE in this study. The occurrence of ototoxicity will however be carefully monitored and stopping rules are in place for excessive ototoxicity (section 13.7).

Serious adverse events must be reported within 24 hours of the knowledge of the event by fax to the National Centre which will notify both the National Study Co-ordinator and the International Data Centre.

The International Data Centre will be responsible for informing the independent Data Monitoring and Safety Committee and other regulatory bodies as appropriate.

In addition, each National Data Centre will be responsible for informing their appropriate national regulatory bodies as appropriate.

### 13. STATISTICAL CONSIDERATIONS

# 13.1 Study design

The study is a comparison between treatment with hyperfractionated radiotherapy and conventional RT with a reduced craniospinal dose in patients with Medulloblastoma without metastases in the age group 4-21 years. The lowest age limit may differ between national groups but must not be lower than 4 years at the day of surgery. Recruitment of patients will last until 31.12.2005. Thereafter a prolongation of the study is possible, (see 13.5), and will be the case in order to recruit the necessary number of patients to reach the desired statistical power. The information of the about the recruitment rate in the HIT study in the first two years of the trial should not be used. A 2-year observation time will be undertaken following closure of the study.

After parental/patient consent every patient in the study will be randomised to one of the two treatment arms. The randomisation will be by block randomisation undertaken at the relevant National Data Centre. Randomisation will be stratified according to sex and the presence of residual tumour (see 5.1.c) on postoperative scan.

GCP of ICH and the Declaration of Helsinki will be respected in the study.

# 13.2 Primary Question

Will hyperfractionated RT lead to a different event free survival (EFS) compared to the standard arm RT?

# 13.3 Secondary Questions

### **All Patients**

1) Will hyperfractionated RT lead to a different progression free (PFS) and overall survival (OS) compared to the standard arm RT?

- 2) Will hyperfractionated RT lead to a different pattern of local tumour control/pattern of relapse with particular respect to local relapse (tumour bed, posterior fossa outside the tumour bed) compared to the standard arm RT? The time to local progression should be the measure for the local tumour control.
- 3) Is there a difference in health status, quality of life index, audiological toxicity and endocrinological late effects in patients treated with hyperfractionated RT compared to patients treated with standard RT?
- 4) The prognostic relevance of biological tumour markers will be studied.
- 5) The toxicity of neurosurgery will be estimated.

# **HIT Group Patients: Additional Secondary Questions**

- 1) Will there be a difference in EFS, PFS and OS in patients with hyperfractionated RT compared to historical similar groups in the HIT-91 study with conventional RT without reduction in the craniospinal dose?
- 2) Is the EFS, PFS and OS in patients with standard RT not worse than the progression free survival in historical similar groups in the HIT-91 study with conventional RT?
- 3) Is there a difference in intelligence quotient in patients treated with hyperfractionated RT compared to patients treated with standard RT?
- 4) Will hyperfractionated RT lead to a difference in degree of leucoencephalopathy compared to conventional RT?
- 5) The following factors should be tested for their prognostic relevance for EFS, PFS and OS:

Histopathological factors

Tumour: preoperative size (biggest diameter in cm)

postoperative size (extent of resection)

localisation/spread

Secondary effects: Hydrocephalus

Occurrence of metastases

Response to RT

Therapy: Quality/Realisation

Age (continuous : age group in years [4-16], [16-21])

Sex

Size of treatment centre i.e. > 4 patients vs < 4 patients yearly

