#### 5.2 Exclusion criteria

- a) One of the inclusion criteria is lacking
- b) Brainstem or supratentorial primitive neuroectodermal tumour.
- c) Large cell medulloblastoma
- d) Atypical teratoid rhabdoid tumour.
- e) Medulloepithelioma.
- f) Ependymoblastoma
- g) Metastatic medulloblastoma (on CNS MRI and/or positive cytospin of postoperative lumbar CSF)
- h) Patient previously treated for a brain tumour or any type of malignant disease.
- i) Patients who are pregnant.
- j) Females who are sexually active and not taking reliable contraception.
- k) Known predisposition to medulloblastoma e.g. Gorlin's syndrome.

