# 13.4 Definitions

i) Event: The appearance of a relapse (local, metastasis or combined) following

previously documented CR, progression (definition below), death for

any reason or the appearance of a secondary tumour.

ii) Progression: If previous residual tumour, growth > 25 % (sagittal and coronal

diameters in axial slice) on neuroradiological investigation or the

appearance of new tumour manifestations.

iii) Event free survival: This time period begins with the day of surgery and ends with the

appearance of an event.

Patients lost to follow-up without an event will be censored at the date

of their last follow-up.

iv) Progression free survival: This time period begins with the day of surgery and ends with the

appearance of a relapse (by previous CR) or progression.

If death occurs that has no relation to the tumour disease or if a

secondary tumour appears the patient will be censored to the time point

when this event occurs.

v) Time to local tumour progression: For the definition of progression see ii. The appearance of

metastases only will not be regarded as local progression.

vi) Quality of life: see Appendix M

vii) Audiological toxicity: see section 10.4.4.

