### HIT Group patients:

- 1. Null hypothesis: The EFS, PFS and OS between patients with HFRT is not different from the EFS, PFS and OS in the historical similar group in the HIT-91 study with standard RT without reduction of the craniospinal dose. These hypotheses should be tested with a two sided log-rank test.
- 2. Null hypothesis: The 4 year EFS-, PFS- and OS-survival rate in patients with standard RT is smaller than the 10% reduced 4 year EFS-, PFS- and OS-survival rate in the historical similar group in the HIT-91 study with standard RT. These hypotheses should be tested with a one sided log-rank-test.
- 3. Null hypothesis: There is no difference in the intelligence quotient in patients with HFRT compared to patients with standard RT. This hypothesis should be tested with a two sided Wilcoxon test for unrelated samples.
- 4. Null hypothesis: There is no difference in the grade of leucoencephalopathy in patients with HFRT compared to patients with standard RT. This hypothesis should be tested with a two sided Wilcoxon test for unrelated samples.
- 5. The importance of the prognostic factors for No. 5 of the secondary questions for HIT Group patients listed in section 13.3 on EFS, PFS and OS will be estimated with Cox-regression analysis.

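### The HIT-group Cox factor list includes metastasis, which is itself an EFS/PFS event, and two post-baseline states that need a landmark or time-dependent analysis

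*Protocol*

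**What the plan says.** Protocol section 13.3, additional secondary questions for HIT Group patients, item 5, opens: "The following factors should be tested for their prognostic relevance for EFS, PFS and OS". The list contains baseline characteristics (histopathology, preoperative tumour size, location and spread, age, sex). It also contains "Occurrence of metastases", "Response to RT" and "Therapy: Quality/Realisation". None of these three has a time point or a definition.

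Section 13.8, HIT Group patients, item 5, gives the method: the factors "listed in section 13.3 on EFS, PFS and OS will be estimated with Cox-regression analysis". It mentions no landmark, no time-dependent term and no restriction to baseline factors.

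Section 13.4 defines the endpoints. For both EFS and PFS, "This time period begins with the day of surgery and ends with the" event concerned. The EFS event includes "The appearance of a relapse (local, metastasis or combined) following" a documented complete remission, and new tumour manifestations count as progression.

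Section 5.2 excludes "Metastatic medulloblastoma (on CNS MRI and/or positive cytospin of postoperative lumbar CSF"). Section 13.8 declares p-values for the secondary questions to be explorative.

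**The concern.** A prognostic factor in a Cox model timed from surgery should be known at surgery, or else enter the model only once it is known. Three listed items do not obviously meet this.

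Metastasis during follow-up is part of the EFS and PFS outcome, so an association with those endpoints is guaranteed and carries no information. Response to radiotherapy and realisation of therapy can be judged favourably only in patients who have stayed event-free long enough to be assessed. If each is coded once per patient and applied from the day of surgery, early failures fall into the unfavourable category by construction.

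At stake is the credibility of the HIT-group prognostic analysis. It could report strong effects that come from the coding alone.

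**Working it through.** The Protocol attaches no figure to this analysis, so there is nothing to reproduce. The check has three parts.

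**1. Metastasis against the endpoint and eligibility definitions**

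- Read as occurrence during follow-up: metastatic relapse or new tumour is an EFS and PFS event (13.4), so every positive patient has an event. In simulations assuming that 60% of events have a metastatic component (not a Protocol figure), an ever/never covariate gives a median HR of about 10 at 70% 3-year EFS and about 23 at 85%. It is significant in 99.9 to 100% of runs.
- Read as stage at diagnosis: metastatic patients are excluded (5.2), so the factor is constant among eligible patients. This reading is also strained because tumour location and spread is a separate item.
- For OS: metastatic relapse is not death, so there is no circularity. It is a post-baseline state.

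**2. When the other two factors become known (days after surgery)**

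- Radiotherapy starts by about day 40 (8.1).
- Standard arm: 30 daily fractions at 5 per week = 42 days (8.7.4), so it ends about day 40 + 42 = 82.
- Pre-chemotherapy MRI just before 6 weeks after radiotherapy (section 9): about day 82 + 42 = 124.
- Courses every 42 days (10.1): course 4 starts about day 124 + 3 × 42 = 250, and course 8 about day 124 + 7 × 42 = 418.

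With constant hazard, P(event before day d) = 1 − S₃^(d/(3 × 365.25)), where S₃ is the 3-year EFS (70% and 85% in 13.10):

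- Day 124: 4.0% and 1.8%.
- Day 418: 12.7% and 6.0%.

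Illustration with 320 patients, 70% EFS and an assumed 80% of event-free patients completing therapy:

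- Early events: 0.127 × 320 ≈ 41, leaving 279.
- Event-free non-completers: 0.2 × 279 ≈ 56.
- Non-realised group: 41 + 56 = 97, of whom 41/97 ≈ 42% are there only because they had already failed.

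**3. Null simulations**

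The settings were exponential EFS, no true effect of the factor, a univariate Cox model from surgery with the factor fixed, and a two-sided 5% test. The size of the HIT subset is not given. The value 168 is 33.6 per year × 5 years, and 77.5% is the mean of 70% and 85%. The shares are assumptions.

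| Factor | n | 3-year EFS | Assumed share favourable | Known at | Median HR | False positives |
|---|---|---|---|---|---|---|
| Realisation | 320 | 70% / 85% | 80% | day 418 | 0.30 / 0.31 | 100% / 99% |
| Realisation | 130 | 70% / 85% | 80% | day 418 | 0.29 / 0.30 | 98% / 79% |
| Realisation | 168 | 77.5% | 70% | about 14 months | 0.40–0.44 | 81–90% |
| Realisation | 168 | 77.5% | 70% | day 250 | 0.58–0.59 | 47–49% |
| Response | 320 | 70% / 85% | 50% | day 124 | 0.80 / 0.82 | 20% / 9% |
| Response | 130 | 70% / 85% | 50% | day 124 | 0.80 / 0.82 | 11% / 6% |
| Response | 168 | 77.5% | 80% | about day 124 | 0.66–0.68 | 25–29% |
| Response | 168 | 77.5% | 50% | day 124 | 0.83–0.84 | 9–11% |

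Ranges at n = 168 are from repeat runs. The response bias grows with the responder share because early failures then make up more of a smaller non-responder group.

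Analysing the same data from a landmark at the time the factor becomes known returns the median HR to 1.00–1.04 with 3 to 5% false positives (n = 320 and 130), and to about 1.0 with 4 to 7% (n = 168).

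**The case against.** The strongest reply is that sections 13.3 and 13.8 name questions and a model class and leave the covariate coding open. Cox regression accommodates landmarks and time-dependent terms, and an analysis plan that is not shown may specify them. This stands for response and realisation: the bias is conditional on fixed coding from surgery, which the Protocol does not state but does not rule out either. It does not rescue metastasis for EFS and PFS, because no coding separates that factor from the event.

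Other parts of the reply also stand:

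- A reader might infer that the metastasis HR cannot be estimated. It can: local relapse, death and second tumours are events too, so the fit is finite but meaningless.
- A reader might infer that metastasis is unusable for OS as well. As a time-dependent covariate it is legitimate there.
- Baseline stage is not strictly constant. Appendix G anticipates patients found metastatic at radiology review. They leave only the per-protocol set (13.9) and stay under intention to treat, so a very small baseline-metastatic subgroup is possible.
- Radiotherapy quality judged on planning films, before or soon after the first fraction (8.8), is close to baseline. The objection is to realisation.
- Realisation need not mean all eight courses. Section 13.9 uses thresholds of 90% of the radiotherapy dose and four cycles. If it meant radiotherapy completion alone (about day 82, 70% share), the null HR is about 0.83 with about 12% false positives.
- A reader might infer that these factors distort the estimates for age, sex or residual tumour. That presumes one joint model, and 13.8 item 5 does not say so.

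**Conclusion.** The point holds in a limited form. The metastasis item conflicts with the Protocol's own event definition and eligibility criteria for EFS and PFS, whatever the coding. Response and realisation are post-baseline. If entered as fixed covariates from surgery, realisation judged at about day 250 to 418 gives a spurious HR of roughly 0.3 to 0.6 with about 50 to 100% false positives, which is a large bias. Response gives 0.66 to 0.84 with about 6 to 29%, which is modest.

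These sizes rest on assumed responder and completion shares, an assumed HIT sample size and constant hazards. The direction of the bias does not depend on the particular values.

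The consequence is bounded. This is an additional, explorative question in one national group. The explorative label covers multiplicity but not circularity. A reader might infer that future risk stratification or the main result is threatened. The Protocol assigns stratification to the biological markers (sections 2 and 3), and the primary EFS comparison is unaffected. The shared age 16 and the missing category for centres with exactly 4 patients a year are editorial. The correction is worth making because the Protocol itself fixes the factor list.

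**What to change.** In sections 13.3 and 13.8 (HIT Group patients, item 5):

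- Remove occurrence of metastases from the EFS and PFS models. For OS, use it only as a time-dependent covariate.
- Analyse response to radiotherapy by landmark at the pre-chemotherapy MRI, among patients event-free at that point.
- Define realisation and the time at which it is judged, and analyse it by landmark at that time or as a time-dependent covariate.
- Restrict the baseline model to factors known at baseline.
- While editing, make the age groups non-overlapping and assign centres with exactly 4 patients a year to one category.

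The cost is a few lines of text, with no new data. The landmark analyses lose patients with earlier events: about 2 to 4% at day 124 and 6 to 13% at day 418 under the Protocol's EFS assumptions.

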# 13.4 Definitions

i) Event: The appearance of a relapse (local, metastasis or combined) following

previously documented CR, progression (definition below), death for

any reason or the appearance of a secondary tumour.

ii) Progression: If previous residual tumour, growth > 25 % (sagittal and coronal

diameters in axial slice) on neuroradiological investigation or the

appearance of new tumour manifestations.

iii) Event free survival: This time period begins with the day of surgery and ends with the

appearance of an event.

Patients lost to follow-up without an event will be censored at the date

of their last follow-up.

iv) Progression free survival: This time period begins with the day of surgery and ends with the

appearance of a relapse (by previous CR) or progression.

If death occurs that has no relation to the tumour disease or if a

secondary tumour appears the patient will be censored to the time point

when this event occurs.

v) Time to local tumour progression: For the definition of progression see ii. The appearance of

metastases only will not be regarded as local progression.

vi) Quality of life: see Appendix M

vii) Audiological toxicity: see section 10.4.4.

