### 13.8 Statistical analysis

The analysis follows the Intention to Treat principle. The main question for the whole cohort of patients and for the HIT group will be analysed in hierarchical order with the analysis of the total group of patients at the top of hierarchy i.e. the significant difference of EFS between both arms of RT for HIT patients can only be achieved if a significant difference of EFS has already been shown for the total group of patients. For the two interim analyses of the main question a significance level of 0.005 will be used in each case. For the final analysis of the main question a significance level of 0.04 will be used. The overall significance level will be equal to 0.05.

The p-value of the tests to answer the secondary questions below will be regarded as explorative.

Corresponding to the main question, the following null-hypothesis and statistical tests will be used:

1. Null hypotheses: The EFS between patients with HFRT and standard RT is not different for the whole group nor for the HIT patients. These hypotheses will be tested with a two-sided log-rank test. Patients will contribute with all their follow up time to the analysis. To illustrate the course of events, hazard and survival function (including the 2, 3 and 5-year survival) in both therapy arms will be estimated.

Corresponding to the secondary questions, the following null-hypotheses and statistical tests will be used:

- 2. Null hypotheses: The PFS and OS in patients with HFRT and standard RT is not different. These hypotheses will be tested with a two sided log-rank test. Patients will contribute with all their follow up time to the analysis. To illustrate the course of events hazard and survival function (including the 2, 3 and 5-year survival) in both therapy arms will be estimated.
- 3. Null hypothesis: The time to local tumour progression in patients with HFRT and standard RT is not different. This hypothesis will be tested with a two sided log-rank test. Patients will contribute with all their follow up time to the analysis. To illustrate the course of events hazard and survival function (including the 2,3 and 5-year survival) in both therapy arms will be estimated.
- 4. Null hypotheses: There is no difference in health status, behaviour, audiological toxicity and endocrinological late effects or quality of life in patients with HFRT compared to patients with standard RT.

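### The 2-, 3- and 5-year survival values for time to local progression will overstate the proportion of patients failing locally if distant-only relapse, death and second tumour are censored; cumulative incidence should be reported beside them

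*Protocol*

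**What the plan says.** Section 13.3, secondary question 2 for all patients, asks whether HFRT changes local control and the pattern of relapse, and names the yardstick: "The time to local progression should be the measure for the local tumour control".

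Section 13.4 v defines the endpoint by reference to progression in item ii and adds that "metastases only will not be regarded as local progression". Item ii covers growth of residual tumour and new tumour manifestations. Death is not part of it. Second tumour is listed apart from progression in item i. Item v gives no rule for a patient who has a distant-only relapse, dies or develops a second tumour. The nearest written rule is for PFS in item iv, where after a death unrelated to the tumour, or if a "secondary tumour appears the patient will be censored to the time point" of that event.

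Section 13.8 item 3 sets the null hypothesis: "The time to local tumour progression in patients with HFRT and standard RT is not different". It continues: "This hypothesis will be tested with a two sided log-rank test" and "Patients will contribute with all their follow up time to the analysis". The description is the one used for EFS, PFS and OS (item 3 differs only in spacing): "hazard and survival function (including the 2, 3 and 5-year survival) in both therapy arms will be estimated". The same section gives the status of these tests: "The p-value of the tests to answer the secondary questions below will be regarded as explorative".

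The protocol mentions neither competing risks nor cumulative incidence.

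**The concern.** For EFS and OS, the survival function at a given time is the proportion of patients still free of the event. That does not carry over to an endpoint that counts only one kind of failure. A patient who relapses in the spine, dies or develops a second tumour leaves the local risk set, or reaches a state in which local failure is no longer comparable. If such patients are censored, the curve describes local failure as it would be if no other failure could occur, with the censored patients keeping the same later local risk as everyone else. That is hard to defend for patients who have relapsed and moved to other treatment.

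At stake is the reading of the 2-, 3- and 5-year values. A reader will take one minus the value as the share of patients who failed locally, and it is larger than that share. The question matters in this trial because section 4.4.3 justifies the tumour-bed boost in the HFRT arm by local relapse. The arms also differ in craniospinal dose (36 versus 23.4 Gy), so the rate of distant relapse may differ between them too.

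**Working it through.** The protocol gives no figure for local progression, so there is nothing of its own to reproduce. The check measures the gap between the two estimates under its planning assumptions.

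**Inputs**
- 3-year EFS of 70% (standard) and 85% (HFRT), with constant hazards: section 13.10.
- All-event hazard h = -ln(EFS at 3 years)/3, which is 0.1189 per year (standard) and 0.0542 per year (HFRT).
- Share c of first events that are non-local: not given for this trial, so assumed to lie between 20% and 80% and to be equal in both arms. Two studies described in the protocol suggest the ends. In CCG-9892 (section 4.4.1), 3 of 14 relapses spared the primary site, or 21%. In the 1999 HFRT study with 30 Gy craniospinal dose (section 4.4.2), the stated 3-year PFS implies 16 × 0.37 + 9 × 0.44 ≈ 10 relapses. Two of these were in the posterior fossa, so about 80% were outside it.

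**Formulas**
- One minus the survival curve, non-local events censored: 1 - exp(-(1-c)·h·t).
- Cumulative incidence of local progression: (1-c)·(1 - exp(-h·t)).

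**Worked example** (standard arm, c = 50%, 5 years)
- One minus the curve: 1 - exp(-0.5 × 0.1189 × 5) = 25.7%.
- Cumulative incidence: 0.5 × (1 - exp(-0.1189 × 5)) = 22.4%.
- Excess: 3.3 points.

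| Arm | Year | Non-local share | One minus curve | Cumulative incidence | Excess (points) |
|---|---|---|---|---|---|
| Standard | 3 | 20% | 24.8% | 24.0% | 0.8 |
| Standard | 3 | 50% | 16.3% | 15.0% | 1.3 |
| Standard | 3 | 80% | 6.9% | 6.0% | 0.9 |
| Standard | 5 | 20% | 37.8% | 35.9% | 2.0 |
| Standard | 5 | 50% | 25.7% | 22.4% | 3.3 |
| Standard | 5 | 80% | 11.2% | 9.0% | 2.2 |
| HFRT | 5 | 20% | 19.5% | 19.0% | 0.5 |
| HFRT | 5 | 50% | 12.7% | 11.9% | 0.8 |
| HFRT | 5 | 80% | 5.3% | 4.7% | 0.5 |

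Excesses are taken before rounding. The excess peaks near a 50% share and falls off on both sides.

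**Does the distant rate drive the curve difference?** Take the same local hazard in both arms, 0.06 per year, and competing hazards of 0.03 and 0.09. At 5 years one minus the curve is 1 - exp(-0.30) = 25.9% in both arms. Cumulative incidence is (0.06/0.09)·(1 - exp(-0.45)) = 24.2% in one and (0.06/0.15)·(1 - exp(-0.75)) = 21.1% in the other. So the cause-specific curves do not move with the distant rate, and cumulative incidence does.

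**Is the excess always larger where competing events are commoner?** No. With local and competing hazards of 0.08 and 0.03, the 5-year excess is 33.0% - 30.8% = 2.2 points. With 0.02 and 0.05 it is 9.5% - 8.4% = 1.1 points, although the competing hazard is higher.

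**The case against.** Four arguments run the other way.

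**The cause-specific analysis is a legitimate target.** Whether HFRT changes local control can be answered by comparing the rates of local failure among patients still at risk, and the log-rank test does that. This stands. A reader might infer that the difference between the arms' curves would partly reflect distant relapse. The documents do not support that: with independent risks the curves depend on the local hazard alone, as the equal-hazard example shows. It is cumulative incidence that shifts with the distant rate, so it should be added and not treated as a purer measure of local control.

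**Censoring is not written.** This also stands. Item v is silent, the only explicit rule belongs to PFS, and the instruction to use all follow-up could mean that patients are still followed for local failure after a distant relapse. The excess would then be smaller, but death would still remove patients from risk and one minus the curve still could not fall below the cumulative incidence. Nor is this merely detail for a statistical analysis plan, because section 13.8 itself names the estimator and the time points.

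**The curves only illustrate.** Section 13.8 offers them to show the course of events and never calls their complement a proportion failing. That is true, but fixed-time survival values invite that reading.

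**A general rule does not follow.** A reader might infer that the overstatement is always greater in the arm with more competing events. It is under the planned event rates with a common non-local share, and at equal local hazards. On the absolute scale it is not so in general.

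**Conclusion.** The point holds in a limited form. If distant-only relapse, death and second tumour are censored, the 2-, 3- and 5-year values cannot be read as proportions with local failure or local control. The excess is about 2.0-3.3 points at 5 years and about 1 point at 3 years in the standard arm, and 0.5-0.8 points at 5 years in the HFRT arm. These sizes rest on the protocol's planned EFS, constant hazards, a non-local share of 20-80% that is assumed to be equal in both arms, and the inferred censoring.

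The log-rank comparison is valid for the cause-specific hazard of local progression. The endpoint is secondary and its p-value exploratory. Primary EFS counts relapse at any site, death and second tumour as events and is not touched. This is a cheap improvement to reporting, not a flaw in the trial's main inference.

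**What to change.** - In section 13.4 v, state how distant-only relapse, death and second tumour are handled, including whether follow-up for local failure continues after a distant relapse.
- In section 13.8 item 3, keep the two-sided log-rank test and label it a comparison of cause-specific hazards.
- In the same item, report the cumulative incidence of local progression at 2, 3 and 5 years by arm, with those three events as competing events.
- Report the cumulative incidence of distant-only relapse by arm beside it, so that a difference in one can be read against the other. This also serves the pattern-of-relapse objective in section 3.

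The cost is a few sentences and one more table. No additional data are needed beyond the date and site of first relapse, death and second tumour, which the EFS and relapse-pattern analyses already require.
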